8.3.1 Primary Efficacy Variable

The primary efficacy variable is the absolute change from baseline for percent predicted FEV_1 at Day 15 in Part 1 and Part 2 Cohort 2A, and through Day 29 in Part 2 Cohort 2B.

The percent predicted FEV_1 is the ratio of FEV_1 (L) to the predicted FEV_1 (L), expressed as a percentage. The predicted FEV_1 will be calculated using the Quanjer GLI-2012 Regression Equations and Lookup Tables, adjusting for age, height, sex and geographic region. Details are provided in Appendix E.

8.3.1.1 Primary Analysis of the Primary Efficacy Variable

The null hypothesis to be tested is that the mean absolute change from baseline in percent predicted FEV_1 (ppFEV₁) is not greater than zero for VX-152 in triple combination (TC) with VX-661/IVA at Day 15 in Part 1 and Part 2 Cohort 2A and through Day 29 in Part 2 Cohort 2B.

Part 1:

The primary analysis will be performed using a mixed-effects model for repeated measures (MMRM) with change from baseline in ppFEV₁ as the dependent variable. This MMRM analysis will include all treatment groups within Part 1, including placebo, VX-152 100mg, VX-152 200mg and VX-152 300mg. The model will include treatment group, visit, and treatment-by-visit interaction as fixed effects, with the continuous baseline ppFEV1 as a covariate, and will include all data from each treatment group and visit up to Day 15. The model will be estimated using restricted maximum likelihood. Denominator degrees of freedom for the F test for fixed effects will be estimated using the Kenward-Roger approximation. A compound symmetry covariance structure will be used to model the within-subject errors. Conditional on the observed data and covariates, missing ppFEV₁ data due to treatment or study discontinuation will be assumed to be missing at random; consequently, no imputation of missing data will be performed.

The adjusted means and 95% confidence intervals (CI) of the treatment effect for each triple combination at Day 15, with a 1-sided P value, will be estimated within MMRM using PROC MIXED in SAS, for all within-treatment and between-treatment comparisons. Contrasts based on the fixed effects in the model, defined at the baseline covariate mean for the combined treatment groups using unique subjects in the FAS who have at least one postbaseline measurement through Day 15, will be used to estimate the treatment effect at Day 15, with the corresponding 1-sided P value for the 1-sided hypothesis test.

Further, the adjusted mean and the 2-sided 95% CI of the treatment difference for withingroup and between-group comparisons at each post-baseline visit up to Day 15 will be provided.

In addition, descriptive analyses of the change from baseline will be performed for all treatment groups by post-baseline visit.

The adjusted mean (with 95% CI) obtained from the MMRM analysis at each post-baseline visit through Day 15 will also be plotted by treatment group. In addition, a waterfall plot showing the subject-level absolute change in ppFEV1 at Day 15 will be presented, by treatment group.

Part 2:

[figure not shown]
A similar MMRM with change from baseline in ppFEV₁ as the dependent variable will be performed separately for each cohort in Part 2. The MMRM analysis will include VX-661/IVA and VX-152 200mg for Cohort 2A, and VX-661/IVA and VX-152 300mg for Cohort 2B.

The adjusted means and 95% CI of the treatment effect for each triple combination at Day 15 in Cohort 2A and through Day 29 in Cohort 2B, with a 1-sided *P* value, will be estimated for all within-treatment and between-treatment comparisons. Contrasts based on the fixed effects in the model, defined at the baseline covariate mean for the combined treatment groups using unique subjects in the FAS who have at least one post-baseline measurement through Day 15 for Cohort 2A and through Day 29 for Cohort 2B, will be used to estimate the treatment effect at Day 15 in Cohort 2A and the average treatment effect through Day 29 (Day 15 and Day 29 only) in Part 2 Cohort 2B, with the corresponding 1-sided *P* value for the 1-sided hypothesis test.

In addition, descriptive analyses of the change from baseline will be performed for all treatment groups by post-baseline visit.

The adjusted mean (with 95% CI) obtained from the MMRM analysis at each post-baseline visit will also be plotted separately for each cohort. In addition, a waterfall plot showing subject-level absolute change in ppFEV₁ at Day 15 for Cohort 2A and at Day 29 for Cohort 2B will be presented, by treatment group.

8.3.2 Analysis of Secondary Efficacy Variables

The secondary efficacy variables include:

- Relative change in ppFEV₁ from baseline at Day 15 (Part 1 and Part 2 Cohort 2A) and through Day 29 (Part 2 Cohort 2B)
- Absolute change in the CFQ-R respiratory domain score from baseline at Day 15 (Part 1 and Part 2 Cohort 2A) and at Day 29 (Part 2 Cohort 2B)

8.3.2.1 Relative change in ppFEV1 from baseline at Day 15 (Part 1 and Part 2 Cohort 2A) and through Day 29 (Part 2 Cohort 2B)

The relative change in $ppFEV_1$ from baseline is defined in Section 8.1. Analysis of this variable will be based on an MMRM model, similar to the primary analysis of the primary efficacy variable. The presentation of results will also be similar.

8.3.2.2 Absolute change in the CFQ-R respiratory domain score from baseline at Day 15 (Part 1 and Part 2 Cohort 2A) and at Day 29 (Part 2 Cohort 2B)

The absolute change in the CFQ-R respiratory domain score from baseline at Day 15 (Part 1 and Part 2 Cohort 2A) and at Day 29 (Part 2 Cohort 2B) will use the 'Adolescents and Adults' Version for ages 14 and above at baseline, and will be based on the *CFQ-R scaled scores*,

For Part 1, the analysis of this variable will be based on an ANCOVA model with treatment as a fixed effect. For Part 2, the analysis of this variable will be based on an MMRM model, similar to the analysis of the primary efficacy variable. The continuous baseline CFQ-R respiratory domain score will be used as a covariate in Parts 1 and 2. The presentation of results will also be similar.

· -	

8.4 Pharmacodynamic Analysis

The sweat chloride measurement for a given visit will be calculated as the mean of the nonmissing sweat chloride measurements obtained on the left and right arms at that visit. If one of the two arm measurements at a time point is missing, the other will be used as the mean. A volume $\geq 15 \ \mu$ L is required for an accurate determination of sweat chloride. Any results reported as having volume <15 μ L will be considered missing. Any sweat chloride values reported as <10 mmol/L or >160 mmol/L will be considered missing.

The analysis of the pharmacodynamic (PD) effect of VX-152 in TC with VX-661/IVA (all parts) on sweat chloride concentrations will be described in this section.

8.4.1.1 Primary Analysis of the Dose Response trend of absolute change in sweat chloride from baseline at Day 15 in Part 1

The null hypothesis to be tested is that the dose response of the mean absolute change from baseline at Day 15 for sweat chloride is not decreasing between placebo and the TC dose groups. The test will be performed using the MCP procedure with the pre-specified contrasts provided in Section 6.2.2.1, within a linear MMRM framework using PROC GLIMMIX in SAS. The model will include treatment group, visit, and treatment-by-visit interaction as fixed effects, with continuous baseline sweat chloride as a covariate. The dose response test will be based on the 1-sided maximum *t*-statistic of the individual *t*-statistics for the multiple pre-specified contrasts at alpha = 5%, based on the treatment group means at Day 15, using a compound symmetry covariance structure for the within-subject errors

The presentation of results for the treatment effect at Day 15, and the treatment effect by visit will be similar to the primary analysis of the primary efficacy variable. The corresponding P value for the decreasing dose response trend will be provided. In addition, descriptive analyses of the change from baseline will be performed for all treatment groups at each postbaseline visit. A waterfall plot showing the subject-level absolute change from baseline in sweat chloride at Day 15 will be presented, by treatment group.

[figure not shown]
8.4.1.2 Absolute change in sweat chloride from baseline at Day 15 (Part 2 Cohort 2A) and through Day 29 (Part 2 Cohort 2B)

The analysis of the absolute change in sweat chloride from baseline at Day 15 (Part 2 Cohort 2A) and through Day 29 (Part 2 Cohort 2B) using the average of Day 15 and Day 29, will be based on an MMRM model fitted to each cohort, separately, similar to the analysis of the primary efficacy variable, with the continuous baseline sweat chloride as a covariate. The presentation of results will also be similar.

The adjusted mean (with 95% CI) obtained from the MMRM analysis at each post-baseline visit in the Treatment Period will also be plotted by treatment group, for each cohort, separately.

In addition, descriptive analyses of the change from baseline will be performed for all treatment groups at each post-baseline visit.

A waterfall plot showing the subject-level absolute change in sweat chloride at Day 15 and Day 29, as applicable, will be presented, by treatment group.

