8.2 Rationale for Study Design and Study Drug Regimens

8.2.1 Study Design

This Phase 2 study is the first clinical study of VX-152 in subjects with CF. It is designed to evaluate the safety of VX-152 in TC with VX-661/IVA and to establish proof-of-concept in 2 populations of subjects defined by *CFTR* genotype: subjects heterozygous for the *F508del-CFTR* mutation with a second *CFTR* mutation not expected to respond to VX-661/IVA (*F508del*/minimal function [MF]) (Part 1) and subjects homozygous for *F508del* (*F508del/F508del*) (Part 2).

Based on in vitro data, TC is predicted to provide clinically relevant improvements in chloride transport in both populations, though the magnitude of response may not be the same in these populations. The subjects will be evaluated by genotype in separate cohorts in Parts 1 and 2, based on the potential for differences in the magnitude of treatment response among these genotype categories. PD will be evaluated through the assessment of sweat chloride, and efficacy will be evaluated through the assessment of spirometry and patient reported outcomes. Part 1 of the study will also obtain information regarding the exposure-response relationship (Section 12.1.2.1).

Placebo is the comparator in Part 1, as efficacy has not been established for a corrector, potentiator, or corrector/potentiator combination in subjects with *F508del*/MF genotypes. VX-661/IVA is the comparator in Part 2, based on the potential for benefit demonstrated for VX-661/IVA in subjects with the *F508del/F508del* genotype in Study VX11-661-101.⁷ Part 2 will have a 4-week run-in period to establish a reliable on-treatment (VX-661/IVA) baseline for comparison to the Treatment Period, when subjects will additionally receive VX-152 or placebo. Off-treatment effects will also be measured at the Safety Follow-up Visit in Part 1 and at the end of the Washout Period in Part 2.

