8.2.2 Study Drug Dose and Duration

Part 1 will evaluate up to 3 dose levels of VX-152 (100, 200, and 300 mg q12h) in TC with VX-661/IVA in subjects with the *F508del*/MF genotype. [REDACTED]

The dose escalation of VX-152 is no more than 2-fold. [REDACTED]

Up to 3 dose levels of VX-152 will be evaluated as part of the TC in Part 1 to provide a range of doses and exposures that will enable dose-response and exposure-response analyses for PD (Section 12.1.2.1). Dose- and exposure-response information obtained from Part 1 (*F508del*/MF genotype) is expected to be applicable to other populations with an *F508del* mutation, including *F508del*/*F508del* genotypes, based on similar in vitro potency for the TC in HBE cells with 1 or 2 copies of *F508del*.⁸

The dose of VX-661 and IVA (100 mg qd and 150 mg q12h) in the TC are the same doses currently under evaluation in Phase 3 studies of VX-661/IVA. These doses of VX-661 and IVA are appropriate for evaluation in the TC based on in vitro experiments with VX-152 which evaluated similar levels of VX-661 and IVA exposure after correction for protein-binding.

[REDACTED]
[REDACTED]
[REDACTED] In
Studies VX06-770-101 and VX11-661-101, improvements in sweat chloride and ppFEV₁ were observed as rapidly as 3 to 7 days after the start of dosing, with most of the effect observed within 14 days. Given the increased in vitro response of the TC relative to VX-661/IVA, it is expected that the 2-week treatment duration will be sufficient to observe differences between treatment arms with respect to efficacy and PD endpoints. In addition, based on previous clinical experience, 2 weeks is sufficient for VX-152, VX-661, and IVA to reach steady-state levels of exposure. The 4-week treatment duration in Part 2 Cohort 2B will provide additional safety data for the TC.

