6 STUDY DESIGN

6.1 Overall Design

This is a Phase 2, 2-part, randomized, double blind, placebo and VX-661/IVA controlled, parallel group, multicenter study designed to evaluate the safety of VX-152 in TC with VX-661/IVA.

Up to approximately 72 subjects with CF are planned for enrollment: up to approximately 36 subjects in each of Part 1 (*F508del*/MF genotype) and in Part 2 (*F508del*/F508del genotype).

Parts 1 and 2 will enroll multiple cohorts, with each cohort evaluating 1 dose level of VX-152 as part of TC with VX-661/IVA (100 mg qd/150 mg q12h). Each cohort will enroll up to approximately 12 subjects in Part 1 and Part 2 Cohort 2A and up to approximately 24 subjects in Part 2 Cohort 2B. Subjects in all cohorts will be randomized 3:1 (active TC:

comparator). Triple placebo will be the comparator in Part 1, and VX-661/IVA will be the comparator in Part 2.

Up to 3 cohorts are planned for Part 1 (Cohorts 1A, 1B, and 1C). Up to 2 cohorts are planned for Part 2 (Cohorts 2A and 2B). The doses of VX-152 planned for evaluation are 100 mg q12h in Cohort 1A, 200 mg q12h in Cohorts 1B and 2A, and 300 mg q12h in Cohorts 1C and 2B. The dose of VX-152 may be adjusted to be lower or the same as the dose level evaluated in the previous cohort.

The actual number of cohorts enrolled in each part may be modified based on emerging safety and PK data. Blinded reviews of safety and available PK data will be conducted by the Vertex study team and lead investigator(s) on an ongoing basis.

[figure not shown]
Cohorts will initiate dosing as follows:

- Cohort 1A will initiate dosing first.
- Cohorts 1B and 2A may initiate dosing if supported by blinded review of safety and available PK data after all subjects in Cohort 1A complete the Day 15 Visit.
- Cohorts 1C and 2B may initiate dosing if supported by blinded review of safety and available PK data after any of the following has occurred:
 - All subjects in Cohort 1B complete the Day 15 Visit.
 - All subjects in Cohort 2A complete the Day 15 Visit.
 - At least 12 subjects across Cohorts 1B and 2A complete the Day 15 Visit.

A schematic of the study design (including the doses of VX-152, VX-661, and IVA to be evaluated) is shown in Figure 6-1.

Figure 6-1 Schematic of the Study Design

Part 1: F508del/MF (up to ~12 subjects per cohort; randomized 3:1)

Part 2: *F508del/F508del* (up to ~12 subjects in Cohort 2A, up to ~24 subjects in Cohort 2b; randomized 3:1)

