6.2.2.1 Pharmacodynamic Effect

The absolute change from baseline at Day 15 in sweat chloride concentrations is a secondary endpoint used to evaluate the PD objective of the study. In Part 1, a test for a decreasing dose-response trend between placebo and the TC dose groups will be performed using a multiple comparisons procedure (MCP). The procedure consists of testing the null hypothesis of a non-decreasing dose-response trend versus a decreasing trend using the 1-sided maximum *t*-statistic that controls the type I error at alpha = 5%. The procedure requires a family of candidate dose-response models to be prespecified, that covers the range of plausible and diverse dose-response profiles.

The candidate models that best describe the expected decreasing dose-response profile of the TC groups compared to placebo include a linear model, a maximum effect (E_{max}) model, and a sigmoid E_{max} model. The contrasts (i.e., linear combinations of the treatment group means

at Day 15) selected to perform the MCP and that capture the shape of these candidate models are described in Table 6-2 below.

Table 6-2	Contrast Coefficients for the Multiple Comparisons
	Procedure in Part 1

Candidate Model	Placebo	Cohort 1A Dose	Cohort 1B Dose	Cohort 1C Dose
Linear	3.0	1.0	-1.0	-3.0
E _{max}	3.0	-1.0	-1.0	-1.0
Sigmoid E _{max}	1.0	1.0	-1.0	-1.0

Note: Contrast coefficients are presented for 2 TC dose groups and placebo.

Table 6-3 provides the power to detect a dose-response trend with the MCP procedure for 3 different expected dose-response profiles with 9 subjects assigned to placebo, 9 subjects assigned to TC in Cohort 1A, 9 subjects assigned to TC in Cohort 1B, and 9 subjects assigned to TC in Cohort 1C for a total sample size of 36 subjects in Part 1 (based on 5000 simulations for each profile using the R software package MCPMod [Version 1.0-8]).

Table 6-3	Power to Detect a Decreasing Dose-response Trend Based on Change
	From Baseline in Sweat Chloride in Part 1

	Mean Change From Baseline in Sweat Chloride				
Candidate Model	Placebo	Cohort 1A Dose	Cohort 1B Dose	Cohort 1C Dose	Power
Linear	0	-12	-16	-20	94%
E _{max}	0	-20	-20	-20	98%
Sigmoid E _{max}	0	0	-20	-20	>99%

Note: A 1-sided maximum *t*-statistic with a sample size of 36 subjects in Part 1 assigned to TC in Cohort 1C, TC in Cohort 1B, TC in Cohort 1A, and placebo at a ratio 1:1:1:1 was used for power calculations. An SD change from baseline in sweat chloride of 13 mmol/L was used for power calculations.

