8.3 Efficacy Analysis

All efficacy analyses described in this section will be based on the FAS, unless otherwise specified. The placebo groups will be pooled across all cohorts in Part 1. The TEZ/IVA groups of varying durations during the Treatment Period (2 weeks and 4 weeks) will be kept separate in Part 2, unless specified otherwise. The analysis will include all available measurements through the last scheduled on-treatment visit including measurements after treatment discontinuation, per the visit windowing rules described in Appendix B. The post-dose measurements on the same day will not be used for any model-based analyses.

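### The Part 1 max-t test takes triple placebo as dose zero, so rejecting it shows that TC differs from triple placebo, not that response rises with VX-152 dose

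*SAP*

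**What the plan says.** SAP 8.4.1.1 sets the null for Part 1 sweat chloride as a Day 15 dose response that "for sweat chloride is not decreasing between placebo and the TC dose groups". It is tested by the largest of three contrast t-statistics, a procedure "that controls the type I error at alpha = 5"% (SAP 6.2.2.1). In the order placebo, 1A, 1B, 1C, the Emax contrast is "3.0 -1.0 -1.0 -1.0". The other two are 3, 1, -1, -3 (linear) and 1, 1, -1, -1 (sigmoid Emax). The P value is to be reported as evidence on a decreasing dose-response trend.

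On the arms, SAP 6.1 states "Triple placebo will be the comparator in Part 1", "with each cohort evaluating 1 dose level of VX-152 as part of TC with VX-661/IVA (100 mg qd/150 mg q12h"). SAP 8.3 adds: "The placebo groups will be pooled across all cohorts in Part 1".

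On purpose, Protocol 8.2.2 says that up to three dose levels are studied "to provide a range of doses and exposures that will enable dose-response and exposure-response analyses for PD", and expects the Part 1 information to carry over to other genotypes with an F508del mutation. Protocol 8.2.1 explains the control arm: "Placebo is the comparator in Part 1, as efficacy has not been established" for a corrector, a potentiator or both in this genotype.

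**The concern.** The step from placebo to any TC group changes three drugs at once, and Part 1 has no VX-661/IVA-only arm. Among the four Part 1 groups, the VX-661/IVA background is constant only across 1A, 1B and 1C. Yet all three contrasts give placebo a positive weight, and the Emax contrast is simply placebo against the average of the TC groups.

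A small P value can therefore arise with no difference at all between VX-152 doses. Under the planned label it would naturally be read as evidence that more VX-152 gives more effect, and Protocol 8.2.2 intends to use Part 1 dose-response information beyond this genotype.

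**Working it through.** **Inputs** (SAP 6.2.2.1, same as Protocol 12.1.2.1): 9 subjects in each of four groups, SD 13 mmol/L, 1-sided 5%, and the three contrasts above. Simplifications for the check: one Day 15 change per subject, normal data, no dropout, pooled variance on 36 - 4 = 32 df. The flat effects other than -20 and the reversed profiles are assumed values.

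**Statistic.** For each contrast c, t = sum(c_i x mean_i) / (s x sqrt(sum(c_i^2)/9)). The test rejects when the largest t exceeds 2.03, the simulated 95th percentile of the maximum when all four means are equal (2,000,000 draws). Rejection rates use 400,000 draws per profile.

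**Step 1: reproduce the plan's power (SAP Table 6-3).**

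| Profile (placebo/1A/1B/1C) | Stated | Recomputed |
|---|---|---|
| Linear 0/-12/-16/-20 | 94% | 94.0% |
| Emax 0/-20/-20/-20 | 98% | 97.7% |
| Sigmoid Emax 0/0/-20/-20 | >99% | 99.5% |

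The check uses the same calculation as the plan.

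**Step 2: identical effect d at all VX-152 doses.** The Emax contrast has expected value 3d and standard error 13 x sqrt(12/9) = 15.01. The standardised signal is 3d/15.01, or about 1.0 at d = 5, 2.0 at d = 10 and 4.0 at d = 20.

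| Common TC effect (mmol/L) | Max-t rejection |
|---|---|
| -2 | 9.5% |
| -5 | 21% |
| -10 | 54% |
| -15 | 85% |
| -20 | 98% |

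The same table applies to a VX-661/IVA effect shared by all TC groups with no VX-152 effect, because the pattern of means is identical.

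**Step 3: reversed order among doses.** For 0/-20/-15/-10, the Emax contrast has expected value 20 + 15 + 10 = 45, and 45/15.01 = 3.0. The max-t test rejects 83% of the time. For 0/-20/-10/0 it rejects about 50% of the time.

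**Step 4: a contrast in which the background is constant.** With equally spaced doses, the linear contrast across the TC groups is 0, 1, 0, -1. This is the 1A-versus-1C difference. Its standard error is 13 x sqrt(2/9) = 6.13.

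| Profile | 1A minus 1C | Difference / 6.13 | Rejection (1-sided 5%) |
|---|---|---|---|
| Any flat TC effect | 0 | 0 | 5% |
| 0/-12/-16/-20 | 8 | 1.31 | 36% |
| 0/-6.7/-13.3/-20 | 13.3 | 2.18 | 69% |
| 0/0/-20/-20 | 20 | 3.26 | 94% |

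The 95% CI half-width is 2.037 x 6.13 = 12.5 mmol/L. That is wider than the 8 mmol/L separating the lowest and highest doses in the sponsor's linear profile.

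**The case against.** The strongest reply is that the test does what it says. Placebo is named in the null, an early-plateau shape is a disclosed candidate model, and the 98% in the Emax row is intended power. That stands. A reader might infer an inflated type I error, and the documents do not support this: the test is valid at 5% for its stated null. The issue is what rejection may be called.

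A reader might also infer that the plan never compares VX-152 doses with one another. That is not so. SAP 8.3.1.1 plans estimates, CIs and 1-sided P values for all between-treatment comparisons in one Part 1 model, and SAP 8.4.1.1 says that the sweat chloride results will be presented similarly. On that reading the 1A-versus-1C comparison will already be produced. What is missing in SAP 8.4.1.1 is any link from the dose-response conclusion to it.

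Thirdly, a reader might infer that VX-661/IVA alone is likely to drive rejection. Protocol 9.1 selects a second allele not expected to respond, and no document gives a background effect size. An unestablished effect is not a zero effect, but its size here is unknown.

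Other mitigations are real but partial. Part 2 compares TC with VX-661/IVA, though in another genotype and without addressing the Part 1 dose trend. Protocol 12.4.2 plans a separate exposure-response analysis. Choice of dose for later cohorts rests on blinded safety and PK reviews, not on this test. The text of Protocol 12.3.4 is absent from the copy available, so the point is confined to SAP 8.4.1.1.

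**Conclusion.** The point holds as one of interpretation and labelling on a secondary endpoint. Rejection supports a TC effect relative to triple placebo. It does not by itself show that response increases with VX-152 dose, or that VX-152 contributes.

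The identical-doses case needs no outside assumption, since the sponsor's own table gives 98% power for a profile flat across doses. The 83% for a reversed order depends on an assumed profile. The background-only case depends on an assumed VX-661/IVA effect: 21% at -5 mmol/L, 54% at -10, and near 5% if that effect is near zero. All rates assume SD 13, 9 per group and a simplified model. The planned MMRM, with its baseline covariate and Day 8 data, would shift them somewhat but not change the logic.

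**What to change.** Keep the max-t test and describe its rejection as TC versus triple placebo.

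In SAP 8.4.1.1, designate the between-dose contrast from the same model, with estimate and 95% CI, as the basis for any statement from this model that response rises with VX-152 dose. The separate exposure-response analysis stands alongside it. Use 0, 1, 0, -1 if the planned equally spaced doses are given. Otherwise set the coefficients from the actual doses, because SAP 6.1 allows later cohorts to use a lower or repeated dose.

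The cost is a few sentences and at most one extra contrast statement, with no new data or model. The downside should be stated in the SAP: a half-width of about 12.5 mmol/L and about 36% power for the sponsor's linear profile mean that a non-significant contrast is not evidence of a flat dose response. The estimate and its interval should carry more weight than the P value.
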